9.1 Adverse events

An AE is any untoward medical occurrence (i.e., any unfavorable and unintended sign [including abnormal laboratory findings], symptom or disease) in a subject or clinical investigation subject *after providing written informed consent* for participation in the study. Therefore, an AE may or may not be temporally or causally associated with the use of a medicinal (investigational) product.

The occurrence of adverse events should be sought by non-directive questioning of the subject at each visit during the study. AEs also may be detected when they are volunteered by the subject during or between visits or through physical examination, laboratory test, or other assessments.

Abnormal laboratory values or test results constitute adverse events only if they fulfill at least one of the following criteria:

- they induce clinical signs or symptoms,
- they are considered clinically significant,
- they require therapy.

Clinically significant abnormal laboratory values or test results should be identified through a review of values outside of normal ranges/clinically notable ranges, significant changes from baseline or the previous visit, or values which are considered to be non-typical in patients with underlying disease. Investigators have the responsibility for managing the safety of individual subject and identifying adverse events. Alert ranges for liver related events are included in [Section 9.3](#).

Adverse events must be recorded on the Adverse Events CRF for subjects that have been randomized into the study. The adverse events should be reported according to the signs, symptoms or diagnosis associated with them, and accompanied by the following information:

1. The severity grade:
 - mild: usually transient in nature and generally not interfering with normal activities
 - moderate: sufficiently discomforting to interfere with normal activities
 - severe: prevents normal activities
2. Relationship to the study treatment
3. Duration (start and end dates) or if the event is ongoing, an outcome of not recovered/not resolved should be reported.
4. Whether it constitutes a serious adverse event (SAE). See [Section 9.2](#) for definition of SAE.
5. Action taken regarding study treatment. All adverse events should be treated appropriately. Treatment may include one or more of the following:
 - no action taken (i.e. further observation only)
 - study treatment dosage adjusted/temporarily interrupted
 - study treatment permanently discontinued due to this adverse event
 - concomitant medication given
 - non-drug therapy given
 - subject hospitalized/subject's hospitalization prolonged
6. Outcome (not recovered/not resolved; recovered/resolved; recovering/resolving, recovered/resolved with sequelae; fatal; or unknown).

Once an adverse event is detected, it should be followed until its resolution or until it is judged to be permanent, and assessment should be made at each visit (or more frequently, if necessary) of any changes in severity, the suspected relationship to the study drug, the interventions required to treat it, and the outcome.

Information about common side effects already known about the investigational drug can be found in the Investigator Brochure (IB) or will be communicated between IB updates in the form of Investigator Notifications (IN). This information will be included in the subject informed consent and should be discussed with the subject during the study as needed.

The investigator should also instruct each subject to report any new adverse event (beyond the protocol observation period) that the subject, or the subject's personal physician, believes might reasonably be related to study treatment. This information should be recorded in the investigator's source documents, however, if the AE meets the criteria of an SAE, it must be reported to Novartis.

9.2 Serious adverse event reporting

9.2.1 Definition of SAE

An SAE is defined as any adverse event (appearance of (or worsening of any pre-existing) undesirable sign(s), symptom(s) or medical conditions(s) which meets any one of the following criteria:

- is fatal or life-threatening
- results in persistent or significant disability/incapacity
- constitutes a congenital anomaly/birth defect
- requires inpatient hospitalization or prolongation of existing hospitalization, unless hospitalization is for:
 - routine treatment or monitoring of the studied indication, not associated with any deterioration in condition
 - elective or pre-planned treatment for a pre-existing condition (that is unrelated to the indication under study) and has not worsened since the start of study drug
 - treatment on an emergency outpatient basis for an event not fulfilling any of the definitions of a SAE given above and not resulting in hospital admission
 - social reasons and respite care in the absence of any deterioration in the patient's general condition
- is medically significant, i.e. defined as an event that jeopardizes the subject or may require medical or surgical intervention.

Life-threatening in the context of a SAE refers to a reaction in which the subject was at risk of death at the time of the reaction; it does not refer to a reaction that hypothetically might have caused death if more severe.

All malignant neoplasms will be assessed as serious under "medically significant" if other seriousness criteria are not met.

Any suspected transmission via a medicinal product of an infectious agent is also considered a serious adverse reaction.

Medical and scientific judgment should be exercised in deciding whether other situations should be considered serious reactions, such as important medical events that might not be immediately life threatening or result in death or hospitalization but might jeopardize the patient or might require intervention to prevent one of the other outcomes listed above. Examples of such events are intensive treatment in an emergency room or at home for allergic bronchospasm, blood dyscrasias or convulsions that do not result in hospitalization or development of dependency or abuse.

All AEs (serious and non-serious) are captured on the CRF and SAEs also require individual reporting to the Drug Safety and Epidemiology Department as per [Section 9.2.2](#).

9.2.2 SAE reporting

To ensure subject safety, every SAE, regardless of causality, occurring after the subject has provided informed consent and until 30 days after the last study visit must be reported to Novartis within 24 hours of learning of its occurrence as described below. Any SAEs experienced after this should only be reported to Novartis if the investigator suspects a causal relationship to study treatment.

Recurrent episodes, complications, or progression of the initial SAE must be reported as follow-up to the original episode, regardless of when the event occurs. This report must be submitted within 24 hours of the investigator receiving the follow-up information. An SAE that is considered completely unrelated to a previously reported one should be reported separately as a new event.

SAEs (initial and follow-up) that are recorded electronically in the Electronic Data Capture system should be entered, saved and e-signed within 24 hours of awareness of the SAE or changes to an existing SAE. These data will automatically be submitted to Novartis Drug Safety & Epidemiology immediately after investigator signature or 24 hours after entry, whichever occurs first. Study site personnel must also inform the Clinical Trial Leader.

Follow-up information provided should describe whether the event has resolved or continues, if and how it was treated, whether the treatment code was broken or not and whether the subject continued or withdrew from study participation. Each re-occurrence, complication, or progression of the original event should be reported as a follow-up to that event regardless of when it occurs.

If the SAE is not previously documented in the Investigator's Brochure and is thought to be related to the investigational treatment a Drug Safety and Epidemiology Department associate may urgently require further information from the investigator for Health Authority reporting. Novartis may need to issue an IN to inform all investigators involved in any study with the same investigational treatment that this SAE has been reported. Suspected Unexpected Serious Adverse Reactions (SUSARs) will be collected and reported to the competent authorities and relevant ethics committees in accordance with EU Guidance 2011/C 172/01 or as per national regulatory requirements in participating countries.

Note: SAEs reported by subjects deemed to be screen failures must be reported to Novartis as outlined here, with appropriate information also captured in the CRFs as specified in the SOM.

9.3 Liver safety monitoring

To ensure subject safety and enhance reliability in determining the hepatotoxic potential of an investigational drug, a standardized process for identification, monitoring and evaluation of liver events has to be followed.

Please refer to [Table 15-1-Appendix 1](#) for complete definitions of liver events.

Follow-up of liver events

Every liver event defined in [Table 15-1-Appendix 1](#) should be followed up by the investigator or designated personnel at the trial site, as summarized below. Additional details on actions required in case of liver events are outlined in [Table 15-2-Appendix 1](#).

- Repeating liver chemistry tests (ALT, AST, TBL, PT/INR, ALP and γ GT) to confirm elevation within 48-72 hours.

These LFT repeats should be performed using the central laboratory if possible. If this is not possible, then the repeats can be performed at a local laboratory to monitor the safety of the patient. Repeats laboratory should then be performed at central laboratory as soon as possible. If a liver event is subsequently reported, any local LFTs previously conducted that are associated with this event should be reported on the appropriate CRF pages.

- If the initial elevation is confirmed, close observation of the subject will be initiated, including consideration of treatment interruption if deemed appropriate.
- Discontinuation of the investigational drug (refer to [Section 7.2](#) Discontinuation of study treatment), if appropriate
- Hospitalization of the subject if appropriate
- Causality assessment of the liver event
- Thorough follow-up of the liver event should include
 - Repeating liver chemistry tests two or three times weekly. Testing should include ALT, AST, ALP, PT/INR, and γ GT. If total bilirubin is elevated $> 2 \times$ ULN, fractionation into direct and indirect bilirubin is required. To rule out muscular origin of transaminase elevations, CPK should be measured along with liver chemistry tests. Frequency of retesting can decrease to once a week or less if abnormalities stabilize or the study drug has been discontinued and the subject is asymptomatic. Retesting should be continued up to resolution.
 - Obtaining a more detailed history of symptoms and prior or concurrent diseases.
 - Obtaining a history of concomitant drug use (including nonprescription medications and herbal and dietary supplement preparations), alcohol use, recreational drug use, and special diets.
 - Exclusion of underlying liver disease, as specified in [Table 15-3](#).
 - Imaging such as abdominal US, CT or MRI, as appropriate
 - Obtaining a history of exposure to environmental chemical agents.
 - Considering gastroenterology or hepatology consultations.

All follow-up information, and the procedures performed must be recorded as appropriate in the CRF.

9.4 Renal safety monitoring

Every renal laboratory trigger or renal event must be followed up by the investigator or designated personnel at the trial site. Recommended follow-up assessments are listed in [Appendix 2](#).

9.5 Reporting Medication errors including misuse/abuse

Medication errors are unintentional errors in the prescribing, dispensing, administration or monitoring of a medicine while under the control of a healthcare professional, subject or consumer (EMA definition).

Misuse refers to situations where the medicinal product is intentionally and inappropriately used not in accordance with the protocol.

Abuse corresponds to the persistent or sporadic, intentional excessive use of a medicinal product, which is accompanied by harmful physical or psychological effects but should not be applicable in this single dose study where treatment is administered under supervision of site staff.

All study treatment errors and uses outside of what is foreseen in the protocol will be collected in the dose administration record. Study treatment errors are only to be reported to Novartis Drug Safety and Epidemiology department if the treatment error is associated with an SAE.

All instances of misuse or abuse must be documented in the Adverse Event CRF irrespective of the misuse/abuse being associated with an AE/SAE. In addition, all instances of misuse or abuse must be reported to Novartis Drug Safety and Epidemiology. As such, instances of misuse or abuse are also to be reported using the SAE form/CRF. [Table 9-1](#) summarizes the reporting requirements.

Table 9-1 Summary of reporting requirements for medication errors

Treatment error type	Document in Dose Administration CRF	Document in AE CRF	Complete SAE form/CRF
Unintentional study treatment error	Yes	Only if associated with an AE	Only if associated with an SAE
Misuse/Abuse	Yes	Yes	Yes, even if not associated with a SAE

For more information on AE and SAE definition and reporting requirements, please see [Section 9.1](#) and [Section 9.2](#), respectively.

9.6 Pregnancy reporting

To ensure patient safety, each pregnancy in a subject on study drug must be reported to Novartis within 24 hours of learning of its occurrence. The pregnancy should be followed up to determine outcome, including spontaneous or voluntary termination, details of the birth, and the presence or absence of any birth defects, congenital abnormalities, or maternal and/or newborn complications. The study drug must be discontinued, though the subject may stay in the study, if she wishes to do so. All assessments that are considered as a risk during pregnancy must not be performed. The subject may continue all other protocol assessments. Pregnancy must be recorded on a Pharmacovigilance Pregnancy Form and reported by the investigator to the local Novartis Drug Safety and Epidemiology Department. Pregnancy follow-up should be recorded on the same form and should include an assessment of the possible relationship to the Novartis study drug of any pregnancy outcome. Any SAE experienced during pregnancy must be reported on an SAE Report Form.

9.7 Early phase safety monitoring

The Investigator will monitor adverse events in an ongoing manner and inform the Sponsor of any clinically relevant observations.

When two or more clinical site(s) are participating in the clinical study, the Sponsor will advise the Investigator(s) at all sites in writing (e-mail) (and by telephone if possible) of any new, clinically relevant safety information reported from another site during the conduct of the study in a timely manner.

10 Data review and database management

10.1 Site monitoring

Before study initiation, at a site initiation visit or at an investigator's meeting, a Novartis representative will review the protocol and CRFs with the investigators and their staff. During the study Novartis employs several methods of ensuring protocol and GCP compliance and the quality/integrity of the sites' data. The monitor will visit the site to check the completeness of subject records, the accuracy of entries on the CRFs, the adherence to the protocol and to Good Clinical Practice, the progress of enrollment, and to ensure that study drug is being stored, dispensed, and accounted for according to specifications. Key study personnel must be available to assist the monitor during these visits.

The investigator must maintain source documents for each subject in the study, consisting of case and visit notes (hospital or clinic medical records) containing demographic and medical information, laboratory data, electrocardiograms, and the results of any other tests or assessments. All information on CRFs must be traceable to these source documents in the subject's file. The investigator must also keep the original informed consent form signed by the subject (a signed copy is given to the subject).

The investigator must give the monitor access to all relevant source documents to confirm their consistency with the CRF entries. Novartis monitoring standards require full verification for the presence of informed consent, adherence to the eligibility criteria, documentation of SAEs, and the recording of data that will be used for all primary and safety variables. Additional checks of the consistency of the source data with the CRFs are performed according to the study-specific monitoring plan. No information in source documents about the identity of the subjects will be disclosed.

10.2 Data collection

Designated investigator staff will enter the data required by the protocol into the CRF using fully validated software that conforms to 21 CFR Part 11 requirements. Designated investigator site staff will not be given access to the electronic data capture system until they have been trained. Automatic validation programs check for data discrepancies and, by generating appropriate error messages, allow the data to be confirmed or corrected before transfer of the data to the contract research organization (CRO) working on behalf of Novartis. The Investigator must certify that the data entered into the CRFs are complete and accurate. After database lock, the investigator will receive a CD-ROM or paper copies of the subject data for archiving at the investigational site.

Data not requiring a separate written record will be defined in the SOM and Assessment schedule (Section 8.1) and can be recorded directly on the CRFs. All other data captured for this study will have an external originating source (either written or electronic) with the CRF not being considered as source.

10.3 Database management and quality control

All data should be recorded, handled and stored in a way that allows its accurate reporting, interpretation and verification.

The CRO working on behalf of Novartis will review the data entered into the CRFs by investigational staff for completeness and accuracy and instruct the site personnel to make any required corrections or additions. Queries are sent to the investigational site using an electronic data query. Designated investigator site staff is required to respond to the query and confirm or correct the data. If the electronic query system is not used, a paper Data Query Form will be faxed to the site. Site personnel will complete and sign the faxed copy and fax it back to CRO working on behalf of Novartis who will make the correction to the database.

Concomitant medications entered into the database will be coded using the WHO Drug Reference List, which employs the Anatomical Therapeutic Chemical classification system. Medical history/current medical conditions and adverse events will be coded using the Medical dictionary for regulatory activities (MedDRA) terminology.

Laboratory samples will be processed centrally and the results will be sent electronically to Novartis (or a designated CRO).

Spirometry will be processed centrally and the results will be sent electronically to Novartis (or a designated CRO).

Randomization codes and data in reference to dispensing of study drug(s) to the subject and all IRT recorded dosage changes will be tracked using Interactive Response Technology (IRT). The system will be supplied by a vendor, who will also manage the database. The database will be sent electronically to Novartis (or a designated CRO).

Each occurrence of a code break via IRT will be reported to the clinical team and monitor. The code break functionality will remain available until study shut down or upon request of Novartis.

The occurrence of any protocol deviations will be determined. After these actions have been completed and the database has been declared to be complete and accurate, it will be locked and the treatment codes will be unblinded and made available for data analysis. Any changes to the database after that time can only be made by joint written agreement between the Global Head of Clinical Information Sciences and the Clinical Franchise Head.

10.4 Data Monitoring Committee

The study will be using a Data Monitoring Committee (DMC). A DMC is a group of professionals, experienced in clinical care and/or clinical research, assembled to provide additional safety oversight to a clinical study. The DMC will consist of four members, with one member being a statistician. The DMC will have a charter completed prior to FPFV and will meet on a regular basis to review safety.

10.5 Adjudication Committee

Not required

11 Data analysis

The analysis will be conducted on all subject data at the time the trial ends. Any data analysis carried out independently by the investigator should be submitted to Novartis before publication or presentation.

11.1 Analysis sets

For all analysis sets, subjects will be analyzed according to the study treatment(s) received.

The safety analysis set will include all subjects that received any study drug.

The PK analysis set will include all subjects with available PK data and no protocol deviations with relevant impact on PK data.

The PD analysis set will include all subjects who received any study drug and have no protocol deviations with relevant impact on PD data. If retrospective review of RHC or echocardiogram data suggests inclusion/exclusion criteria may not have been met, additional subjects may be excluded from the PD analysis set.

Data from the two parts of the study will be pooled for the statistical analysis and treatment groups will be defined as QCC374 and placebo.

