6.2 Treatment arms

Subjects will be assigned to either the QCC374 or Placebo treatment arms in a ratio of 3:1 in Part 1 and ratio of 2:1 in Part 2. Refer to [Section 3.1](#) and [Section 3.2](#) for information on dosing schedule and rationale.

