6.3 Treatment assignment and randomization

Randomized treatment will be assigned to individual subjects by way of a randomization number, which will be in the range of 5101-5108 for Part 1 and 5201-5252 for Part 2. The availability of 60 randomization numbers is chosen here as the sample size may be increased at the IA.

The randomization number is only used to identify which treatment the patients have been randomized to receive. The Subject number assigned to a subject at screening remains the unique identifier for the subject throughout the study. For information on subject numbering, please see 'Subject numbering' section in the SOM.

All eligible subjects will be randomized via Interactive Response Technology (IRT) to one of the treatment arms. The investigator or his/her delegate will use the IRT system after confirming that the subject fulfills all the inclusion/exclusion criteria. The IRT will assign a randomization number to the subject, which will be used to link the subject to a treatment arm, and will specify a unique medication number for the first package of investigational treatment to be dispensed to the subject.

The randomization numbers will be generated using the following procedure to ensure that treatment assignment is unbiased and concealed from subjects and investigator staff. A subject randomization list will be produced by the IRT provider using a validated system that automates the random assignment of subject numbers to randomization numbers. These randomization numbers are linked to the different treatment arms, which in turn are linked to medication numbers. A separate medication list will be produced by or under the responsibility of Novartis Drug Supply Management using a validated system that automates the random assignment of medication numbers to packs containing the investigational drug(s).

The randomization scheme for subjects will be reviewed and approved by a member of the Randomization Office. Follow the details outlined in the SOM regarding the process and timing of treatment assignment and randomization of subjects.

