11.4.2 Statistical model, hypothesis, and method of analysis

The change from baseline (on log transformed values) will be analyzed using an ANCOVA model with treatment as a factor and log transformed baseline PVR as a covariate. Likelihood based posterior distributions will be derived to assess the probability that QCC374 is better than placebo and the probability that the reduction vs placebo is at least 15%.

Corporate Confidential Information

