11.7 Sample size calculation

We assume around 20% dropout, which should provide complete PVR data from around 30 patients (approximately 10 on placebo and approximately 20 on QCC374), if approximately 38 patients are randomized. Corporate Confidential Information

Corporate Confidential Information

If the true effect is 20% over placebo, then the probability to meet the efficacy criteria is 80%.
If the drug effect over placebo is 0, then there is 40% chance of declaring futility at the IA.
If the drug effect over placebo is 0, then the chance of declaring efficacy is 9% at the end of the study.

Corporate Confidential Information

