 - Model estimated treatment comparison of PVR at Week 16
 - Raw geometric mean of PVR by treatment over time
 - Model estimated treatment comparison of 6MWD at Week 16
 - Raw arithmetic mean (SD) of 6MWD by treatment over time
 - Group summary plot of Hemodynamic parameters other than PVR by treatment over time
 - Group summary plot of Right ventricular (RV) function parameters with echocardiography (other than PVR) by treatment over time

4 Statistical methods: Analysis sets

For subjects for which the actual treatment received does not match the randomized treatment the treatment actually received will be used for the analysis.

The safety analysis set will include all subjects that received any study drug.

The PK analysis set will include all subjects with at least one available valid (i.e. not flagged for exclusion) PK concentration measurement, who received any study drug and experienced no protocol deviations with relevant impact on PK data.

The PD analysis set will include all subjects with any available PD data, who received any study drug and experienced no protocol deviations with relevant impact on PD data. If retrospective review of RHC or echocardiogram data suggests inclusion/exclusion criteria may not have been met, additional subjects may be excluded from the PD analysis set.

Data from the two parts of the study will be pooled for the statistical analysis and treatment groups will be defined as QCC374 and placebo.

The analysis sets and protocol deviation codes are related as follows:

Table 4-1 Protocol deviation codes and analysis sets

Category Deviation code	Text description of deviation	Data exclusion
Subjects are excluded from PK analysis in case of these PDs:		Exclude subject from PK analysis set
INCL##	Xxxxxxx	
EXCL##	Xxxxxxx	

Category Deviation code	Text description of deviation	Data exclusion
Subjects are excluded from PD analysis in case of these PDs:		Exclude subject from PD analysis set
INCL##	Xxxxxxx	
EXCL##	Xxxxxxx	
Subjects are excluded from PK and PD analysis in case of these PDs:		Exclude subject from PK and PD analysis sets
INCL##	Xxxxxxx	
EXCL##	Xxxxxxx	

If updates to this table are needed, an amendment to the SAP needs to be implemented prior to DBL.

5 Statistical methods for Pharmacokinetic (PK) parameters

All subjects within the PK analysis set will be included in the PK data analysis.

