6.1.3 Statistical model, assumptions and hypotheses

The change from baseline (on log transformed values) will be analyzed using an ANCOVA model with treatment as a factor and log transformed baseline PVR as a covariate. Likelihood based posterior distributions, based on model adjusted means and assuming a t-distribution, will be derived to assess the probability that QCC374 is better than placebo and the probability that the reduction vs placebo is at least 15%.

The following criteria will be assessed as a guide to decision making:

Efficacy criteria at Interim analysis:

- If there is at least 90% probability that the treatment effect of QCC374 is better than placebo in PVR and
 - If there is at least 50% probability that the reduction in PVR is at least 15% (corresponding to a ratio of 0.85) in favor of QCC374 compared to placebo.
- Corporate Confidential Information

Corporate Confidential Information

Efficacy criteria at End of Study:

- If there is at least 90% probability that the treatment effect of QCC374 is better than placebo in PVR and
- If there is at least 50% probability that the reduction in PVR is at least 15% in favor of QCC374 compared to placebo.

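### The primary PVR analysis pools two separately randomised Parts with no Part term, and no visible output gives a Part 2 estimate beside the pooled ratio

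*Protocol*

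**What the plan says.** Both documents pool the Parts. Protocol 11.1 has "Data from the two parts of the study will be pooled for the statistical analysis and treatment groups will be defined as QCC374", with placebo as the other group. The synopsis agrees, and SAP section 4 repeats "Data from the two parts of the study will be pooled for the statistical analysis".

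Assignment is done separately by Part. Protocol 6.3 gives each Part its own randomisation numbers, "which will be in the range of 5101-5108 for Part 1 and 5201-5252 for Part 2", and Protocol 6.2 allocates "in a ratio of 3:1 in Part 1 and ratio of 2:1 in Part 2". The notes to Protocol Figure 3-2 set the maximum dose at 0.12 mg bid in Part 1 and 0.06 mg bid in Part 2.

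The primary model in Protocol 11.4.2 and SAP 6.1.3 is an "ANCOVA model with treatment as a factor and log transformed baseline PVR as a covariate". SAP 6.1.3 introduces its rules with "The following criteria will be assessed as a guide to decision making". QCC374 must be better than placebo with probability 90% or more, and there must be "at least 50% probability that the reduction in PVR is at least 15% (corresponding to a ratio of 0.85"). The same two rules are listed for the interim and for the end of study. SAP 6.1.3.3 presents one pooled ratio with an 80% confidence interval.

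SAP 6.2.4 allows optional analyses by smoking status, by mono- versus combination therapy, with background therapy as a covariate, and by the dose mostly received. None is by Part. SAP sections 2 and 7.1.2 tabulate doses. Text is blacked out next to Protocol 11.4.2, SAP 6.1.3 and SAP 6.2.4, so these statements cover the visible text only.

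**The concern.** There are two separate points.

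- **Stratum.** Part determines a patient's chance of receiving QCC374, so it acts as a randomisation stratum even though neither document uses that word. A model without Part lets any difference in PVR change between Parts leak into the treatment contrast.
- **Mixture.** Under the protocol's dose caps, the pooled ratio averages two regimens. A posterior probability of at least 50% for a ratio of 0.85 or less amounts to a point-estimate cut at 0.85. Near that cut, a different effect in the few Part 1 patients can move the pooled result across it, and nothing visible would show this. Dose tabulations describe the mix. A split by dose received depends on tolerability after randomisation. Only a contrast within Part 2 is a randomised comparison under the Part 2 cap.

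**Working it through.** **Plan's own figure.** Protocol 11.7 expects "complete PVR data from around 30 patients" at 20% dropout: 30/0.8 = 37.5, so 38. This reproduces. The stated 80% and 9% cannot be checked, because the SD and the interim rules are not visible.

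**Inputs.** Part 1: 6 QCC374, 2 placebo. Part 2: about 20 and 10. Maximum 60 randomised. The 30-completer case uses an assumed split of 5/2 + 15/8.

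**Part 1 share of the pooled QCC374 effect** (Part 1 QCC374 / all QCC374):
- planned: 6/26 = 23.1%
- 30 completers: 5/20 = 25%
- N = 60: 6/40.67 = 14.8%

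**Allocation bias.** 6/26 − 2/12 = 0.064. A 0.1 log difference in PVR change between Parts therefore shifts the unadjusted contrast by 0.0064 log, about 0.6% of the ratio. At assumed interim sizes of 12 to 24 patients the shift is 0.009–0.010.

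**SE cost of a Part term** (information = a·p/(a+p), for a QCC374 and p placebo patients):
- pooled: 26×12/38 = 8.211
- by Part: 6×2/8 + 20×10/30 = 8.167
- SE ratio: √(8.211/8.167) = 1.0027
- one / both Part 1 placebo patients without week 16 PVR: 1.0136 / 1.0408
- expected at 20% independent dropout: 0.64×0.27 + 0.32×1.36 + 0.04×4.08 = 0.77%

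With Part in the model, Part 1 still has weight 1.5/8.167 = 18.4%, against 23.1% without it. A Part term alone does not separate the regimens.

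**Part 2-only precision.** The SE ratio to pooled is √(8.211/6.667) = 1.110, and the 80% CI is 1.116 times as wide (27 versus 35 df). With 30 completers these are 1.130 and 1.140. At assumed interims of 12, 15, 20 and 24 patients, with Part 1 complete, Part 2 supplies about 1, 2, 4 and 5 placebo patients. The Part 2 CI is then 3.7, 1.6, 1.3 and 1.2 times as wide.

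**Mixture, expected values.** With assumed ratios of 0.75 in Part 1 and 0.87 in Part 2, and equal placebo change, the pooled ratio is 0.75^0.231 × 0.87^0.769 = 0.841. This is below 0.85 although Part 2 is not.

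**Mixture, simulation.** 30,000 trials per setting, 5/2 + 15/8, assumed residual SD, ANCOVA with one baseline covariate. Success means an estimated ratio below 0.85 and a one-sided t criterion at 90%. The table gives the share of trials with criteria met but a Part 2 estimate above 0.85.

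| True ratio, Part 1/Part 2 | SD 0.20 | 0.25 | 0.30 | 0.35 |
|---|---|---|---|---|
| 0.70/0.90 | 27.6% | 22.8% | 18.2% | 12.6% |
| 0.80/0.86 | 12.6% | 11.5% | 10.2% | 7.4% |
| 0.849 in both | 8.0% | 8.0% | 7.0% | 5.5% |
| 0.846 in both | 8.1% | 7.9% | 7.3% | 5.7% |

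The common ratios were chosen to give about the same pass rate. The excess over chance is 2–5 points in the milder case and 7–20 in the steep one. The reverse (criteria missed while Part 2 alone meets both) occurs in about 1% of trials at 0.70/0.90, 4% at 0.80/0.86 and 5–8% with a common ratio. Adding Part lowers the pass rate by 2–5 points at 0.70/0.90 and by about 1 point at 0.80/0.86.

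**The case against.** The strongest case is that this is a reporting preference. Pooling is deliberate and stated three times. The study is non-confirmatory and its criteria only guide a decision. Allocation bias is negligible, and a Part term barely changes Part 1's weight. If both Part 1 placebo patients lack week 16 PVR (a 4% chance), a Part term takes every Part 1 QCC374 patient out of the treatment contrast. In the milder scenario, disagreement between the pooled and Part 2 results in either direction totals about 11–17%, against 11–16% when the Parts do not differ. A discordant Part 2 ratio would then usually be noise. The steep scenario is invented. Patient listings and number ranges would let anyone compute a Part 2 ratio later, and blacked-out text may already plan one.

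Most of this stands, and it limits the weight of the point. Part is also an imperfect proxy for dose, because Protocol 3.1.1 lets Part 1 patients stay below 0.12 mg. SAP 1.4 gives both Parts the same 0.12 mg bid target; if that governed, only the stratum argument would remain. None of this gives a reason to leave out of the model the factor that set the allocation ratio, when including it costs almost nothing. Nor does an optional split by dose received replace a randomised Part 2 contrast specified in advance.

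**Conclusion.** The point holds on the visible text and is modest. The missing Part term causes little bias, so that change rests on matching the analysis to the randomisation at low cost. The more useful gap is the missing Part 2 estimate: about a quarter of the pooled effect comes from Part 1, which has a different protocol dose cap, and the decision turns on a cut at 0.85. How often this would mislead depends on a contrast between Parts, a residual SD and interim sizes that are all assumed here. Part 1's share at the interim is larger, because Part 2 starts only after Part 1 patients have had two weeks of dosing. Its size is unknown, because the interim timing is blacked out.

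**What to change.** 1. Add Part (1 or 2) as a factor in the primary ANCOVA. The cost is one degree of freedom and, if the Parts do not differ, 0.3% on the SE at planned numbers (about 0.8% expected after dropout).
2. At end of study, report the Part 2-only QCC374/placebo ratio with 80% CI as supportive, not as a gate, with evaluable counts per Part and arm. At the interim, show the counts, and give a Part 2 ratio only above a prespecified minimum of evaluable Part 2 placebo patients. Five is one example; its 80% CI would be about 24% wider than the pooled one.
3. Label any split by dose received as non-randomised.

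All three need only SAP wording and one extra output.

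Separately, and adding no weight to this point, the Part 2 dosing passages must be reconciled. SAP 1.4, written when protocol V01 was available, differs from Protocol 3.1.2 on both the starting dose and the target. Within the protocol, 3.1.1 states a 0.06 mg starting dose for Part 2, while the synopsis, 3.1, 3.1.2 and 3.2 state 0.03 mg. This review takes no view on which is right.
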